22 March 2021

Dear Sir/Madam,

Official Title: A Controlled trial of Yoga in Pediatric Inflammatory Bowel Disease

NCT No: NCT03338894

Date of document: 14 February 2021

I am writing to provide the updated study protocol of the above said study. The protocol document has been approved by the Institutional Review Board.

Thank you

[name]

Title of Project:

A Controlled trial of Yoga in Pediatric Inflammatory Bowel Disease

PI: [name]

Co-investigators: [name]; [name]; [name]; [name], DO; [name]; [name]; [name]; [name], APN; [name]; [name], DO; [name]; [name]

Lay Summary:

Approximately 25% of Inflammatory bowel disease (IBD) is diagnosed in the pediatric age group, with the peak age of onset in the adolescent years¹. IBD adds additional stressors of a chronic disease with unpredictable and potentially embarrassing symptoms to the expected challenges of psychological and social adjustment that teenagers face. Various techniques, such as psychotherapy programs and IBD overnight camp experiences, have been studied to decrease psychological distress and improve quality of life. Stress, and particularly how stressful events are perceived, may play a role in triggering IBD flares. Complementary and alternative medicine (CAM), especially mind-body techniques are used often by pediatric IBD patients and may be beneficial in decreasing stress and improving quality of life (QOL). Yoga may be well suited as an adjunct to conventional IBD therapy to decrease stress, provide a greater sense of bodily control and improve QOL.

The primary goal of this project is to determine if a structured Yoga program, in addition to standard medical therapy, improves HRQOL in pediatric patients diagnosed with inflammatory bowel disease (IBD). We will also examine if the yoga program improves self-efficacy, which is a person's belief about their ability to influence events that affect their lives. Disease response and remission rates will be followed as well, in order to stratify HRQOL outcomes in the yoga group.

Patients will each serve as their own control and complete questionnaires at enrollment and at the start and end of the 12-week group yoga class sessions. They will also complete the questionnaires three months after finishing the class sessions. . The program will consist of a live group class session over 12 weeks. Baseline and follow-up questionnaires will be used to determine there are changes in QOL, self-efficacy, and disease response.

I. Specific Aims:

1. Primary Aim: To determine if a structured Yoga program, in addition to standard medical therapy, improves health related quality of life (HRQOL) in pediatric patients diagnosed with IBD

2. Secondary Aim:

To determine if, in pediatric patients recently diagnosed with IBD, a structured Yoga program:

- Improves self-efficacy

II. Background and Significance:

Approximately 25% of Inflammatory bowel disease (IBD) is diagnosed in the pediatric age group with the peak age of onset in the adolescent years¹. Adolescence is a time of great psychosocial growth. IBD adds additional stressors of a chronic disease with unpredictable and potentially embarrassing symptoms. Side effects of steroid treatment, such as acne, weight gain, and mood changes, as well as delayed puberty, may further ostracize youth with IBD. The incidence of psychiatric disorders, is increased compared to healthy children and is comparable to other chronic diseases such as cystic fibrosis². HRQOL may be impaired by issues of pain, school absences, and concerns about the chronic nature of IBD and patients with increased disease severity often have worse HRQOL².

Various strategies have been tried to improve HRQOL and psychosocial functioning in pediatric IBD patients. A prospective analysis of HRQOL and anxiety in children attending a one week camp sponsored by the Crohn's and Colitis foundation of America demonstrated improvement in the quality of life³. A cognitive behavioral therapy (CBT) program, which included relaxation training and pain-coping strategies, increased a feeling of control and decreased helplessness in adolescents⁴. More recently a skills based psychological intervention program, which included relaxation, imagery and deep-breathing as part overall CBT program, showed significant reductions in somatization symptoms in a group of adolescent girls with IBD and their parents when pre and post-treatment variables were compared⁵.

The role that stress may play in triggering flares of IBD has been investigated in the adult IBD population. Stress has been shown to alter gut permeability and cause the release of neuropeptides with immune modulatory effects⁶. Although some studies suggest conflicting results, several prospective studies have found a positive association with stress and IBD flares, particularly the perception of stressful events, as opposed to discrete events⁶.

Complementary and alternative medicine (CAM) use in pediatric IBD patients ranges from 40-50%⁷⁻¹⁰. Heuschkel et al reported that 41% of IBD patients used CAM because of adverse effects from conventional medications and 59% of respondents not using CAM were interested in learning more about it⁹. In a similar study by Day et al, 72% of children with IBD were noted to have tried CAM therapies, often due to parental frustration with managing their child's illness. Use of CAM was increased particularly in patients with worse QOL^{8, 11}. Mind-Body CAM techniques, especially relaxation, meditation and prayer are popularly used by adolescents with IBD and patients with more severe disease are more willing to consider relaxation strategies¹¹.

Yoga is a mind-body practice that originated in India more than 2000 years ago and is used by greater than a million children in the United States¹². Rates of yoga use in pediatric IBD patients are low^{8, 11}, with one study reporting only 1.4 % use⁸. This presents an opportunity to explore this underused CAM modality in pediatric IBD. Yoga may be well suited as an adjunct to conventional IBD therapy to decrease stress, provide a greater sense of bodily control, and improve HRQOL.

III. Preliminary Studies/Progress Report:

There have not been any studies to date looking at the role of Yoga in IBD. A recent systematic review of the clinical applications of yoga in the pediatric population found 34 studies¹², including a number for psychological health, as well as one for irritable bowel syndrome¹³ which suggested benefit. Unfortunately, many studies suffered from low methodological quality secondary to lack of randomization and inadequate statistical analysis¹².

IV. Research Design and Methods:

Participants and Enrollment:

The study will prospectively enroll patients seen at the Pediatric IBD center of the Goryeb Children's Hospital. All pediatric patients diagnosed with IBD will be offered enrollment in the study. Data collection surveys will be initially completed at the time of consent (time 0), start of the yoga (time 1) session, end of the yoga session (time 2) and three months after completion (time 3) to determine if the effects of yoga are lasting. Each patient will serve as their own control with the difference between time of enrollment (time 0)/start of yoga (time 1) and start of yoga (time 1)/end of yoga (end of 2) being compared. Patients will enroll in a twelve class series offered twice a year. The classes will be open to a maximum of ten students and will continue to be offered once a week with encouragement to practice daily at home. Patients will have the option to attend a fall or spring set of classes to increase flexibility and improve enrollment.

Through the entire study period patients will receive standard medical therapy as determined by their specific pediatric gastroenterologist. Clearance by their primary gastroenterologist will be required in the 8 week time period prior to starting yoga to confirm they are healthy enough to start yoga.

Sample Size: Based on what has been determined to be the minimal clinically significant difference¹⁴ of HRQOL using the pedQL survey, we would need 34 patients in total as each patient will serve as their own control. . With a sample size of 34 patients, there will be 80% power to detect a 10-point increase (improvement) in average total PedsQL score (0-100 scale)]. The sample size calculation was based on standard deviation of the total score in the Control group = 15.4, probability of Type I error (alpha) of 0.05, and probability of Type II error (beta) of 0.20. That is, in only 20% of the times we will fail to reject the null hypothesis when it is in fact false; i.e. there is a difference.

Recruitment will be feasible over a two-year study time frame as we care for over 800 active IBD patients in our center.

Inclusion Criteria:

- Both male and female patients with IBD.
- Age 10-17 years
- Not currently practicing specific mind-body techniques (yoga, pranayama, biofeedback, hypnosis, guided imagery)
- Diagnosis of IBD

Exclusion Criteria: Other Chronic systemic disease ex. RA, CF, Celiac. Any chronic neurologic condition.

Yoga Introduction:

Yoga is one component of Ayurveda, which is the complete traditional system of healthcare practiced in India and Sri Lanka. Understanding an individual's constitution and energy is a key part of Ayurvedic medicine. Each person's constitution is felt to be a balance of three types of energy, also known as the doshas. In Ayurveda, inflammatory disorders of the gut are primarily due to an imbalance of 'pitta' dosha of the Anna Vaha Srotas (Digestive System). Anna vaha srotas has the important functions of digestion, absorption, and assimilation. Anna vaha srotas and respiration have integrated functioning according to Ayurveda. If one breathes deeply, it increases the secretion of digestive enzymes. People who do pranayama (deep breathing regularly, in general tend to have a strong appetite, because pranayama stimulates anna vaha srotas agni (digestive fire).

Pitta pacifying poses include forward bends and twisting yoga poses stimulate the digestive system. Forward bends are calming and reduce stress. Inversions stimulate the endocrine system. All of these effects are felt to be beneficial for a healthy digestive system.

Our yoga program will consist of a 12 week program, one class session per participant, per week. Classes will be offered once a week at Goryeb Children's Hospital/Atlantic Health System, Morristown, NJ. Classes will be one hour in duration. We will offer two sessions a year.

The yoga teacher will be certified in Hatha yoga, which is the most common form in America, and be registered with the Yoga Alliance. We will require a minimum of 500 training hours.

Yoga Class description:

WARM UP/COOL DOWN:

- Breathing Techniques, Relaxation-Guided Imagery, Progressive Muscle Relaxation
- Yoga poses - see appendix 1

- Contraindications: Glaucoma, neck injury
- Poses will be modified to adjust for these contraindications

MODIFICATIONS TO ROUTINE:

Certain symptoms dictate modification of some of the yoga poses. All patients will be advised at the start of class to inform the teacher if they are menstruating, have nausea/vomiting, are dizzy, or are experiencing severe pain/flare/active bleeding. Patients will also be reminded to let the teacher know if they have a cold/cough/bronchitis/asthma exacerbation on the day of class, or if they have had a recent neck/back injury. They may be instructed not to participate in class at all that day, or to refrain from participating in certain asanas/poses that day.

The teacher will present modifications to the routine (such as avoiding inverted poses) for patients who are menstruating or having an active flare of GI symptoms.

Data collection measures :

- Impact III:

This is a validated, disease-specific pediatric questionnaire that measures HRQOL in pediatric IBD¹⁶ patients age 9-17 years. It consists of 35 questions and six domains: IBD symptoms, systemic symptoms, emotional functioning, social functioning, body image, and treatment/interventions. The answers are scored on a 5 point Likert response scale.

- Peds QL:

This is a validated pediatric questionnaire that measures general HRQOL in children ages 8-17 years¹⁴. It consists of 23 questions in areas of social, school, emotional and physical functioning. The answers are scored on a 5 point scale and then reverse scored and linearly transformed to a 0-100 scale.

- General Self-Efficacy Scale:

This is a widely used simple 10 item scale that measures a patient's a general sense of perceived self-efficacy, aiming to predict coping with daily life as well as adaptation after stressful life events¹⁷. It is a measure that has been validated in adolescents age 12 and above.

- PCDAI and PUCAI :

The Pediatric Crohn Disease Activity Index (PCDAI) and Pediatric Ulcerative Colitis Activity Index (PUCAI) are validated disease activity indices that include patient symptoms in the previous seven days, physical exam findings, growth parameters

and laboratory studies¹⁸. The information needed to complete this index will be available through the patient's chart as the data collected is part of routine care.

- Physician Global Assessment :

This is a global assessment is part of routine care and determined by the patient's primary GI doctor. The assessment is a global measure of disease activity with the following five categories: inactive, mild, moderate, severe, NA/unknown.

- Short Crohn Disease Activity Index (SCDAI):

This tool has been validated for use in adult crohn's disease patients but is particularly useful for measurement of short-term disease activity and wellbeing. This data will be collected in the crohn's disease patients and includes liquid stools, well-being and abdominal pain²⁵.

- Medication use data:

We will record what medications the patient is currently using, including steroids, biologics and immune modulators. The dose of medications will also be recorded in order to determine such information as the total dose of steroids, per patient over the study period.

- Yoga Questionnaire:

The yoga questionnaire will consist of questions about past exercise experience, use of other non-mind/body CAM such as probiotics, herbs and supplements. Post yoga the questionnaire will consist of questions if they plan to continue to practice after the study is complete.

- Follow up questionnaire:

Questionnaire will be sent for those subjects who have completed at least nine classes. The follow up questionnaire consists of 5 questions to evaluate if they are still practicing yoga, any benefit from being in the yoga study, has it helped manage their IBD and would they participate in a follow up yoga study.

In addition to the questionnaire/outcome measure collected at baseline and at the different endpoints (Impact III, peds QL, self efficacy scale, PCDAI, PUCAI), baseline demographic and clinical data will be gathered for each patient in the study. Those include age, gender, race, disease type (crohn's, UC), date of diagnosis, areas of bowel involved, medications and dose of steroids.

V. Planned Data Analysis:

Baseline demographic data will be collected and descriptive statistics will be used to profile the patient population. Clinical factors collected at baseline and post intervention and the differences will be

analyzed between the yoga and control group. Categorical data will be analyzed using chi-square or Fisher's exact tests. The distribution of all continuous data will be examined. For continuous variables whose distributions approximate normality, a t-test will be used for comparisons. When normality assumptions are not satisfied, the non-parametric Mann-Whitney U test will be utilized.

The data from the questionnaires will be collected via REDCap secure access.

Statistical significance is considered at $p < 0.05$. All statistical analyses will be performed using MINITAB 17.

VI. Benefits and Risks:

We anticipate the participants who complete the yoga program will have improved HRQOL and self-efficacy. All participants may experience a personal satisfaction by their contribution to a clinical investigation.

We anticipate minimal risk from participation in the yoga program. A systematic review of yoga in the pediatric population found no adverse events reported and suggested that yoga was a low-risk intervention¹². Hatha Iyengar yoga is a very low-intensity physical activity and is less taxing on the cardiovascular system than walking¹⁹. There have been rare case reports of complications following yoga and these were primarily neurologic in origin²⁰⁻²². Patient with any chronic underlying neurologic condition will be excluded. There will be formal "live" instruction to assist in proper technique of the poses.

VIII. Human Subject/Ethical Issues

After the investigators have entered the data from outcome measure questionnaires, all further analysis will be done with "de-identifiable information". All personal identifiers (name, date of birth, medical record number, address etc.) will be removed. Only the previously mentioned investigators will have access to the master list that associates the child's answers to personal information that he or she could be identified with. All data will be kept on a password protected computer database/REDCap secure access. Data will be entered into the database using the alphabetical/numeric codes. A copy of the signed parental permission form will appear in the patient's medical record. The original completed questionnaires will be kept in a locked filing cabinet in the principal investigator's office. The identity of the subjects will not be disclosed in any publication related to this study.

IX. Data Safety Monitoring Plan

The principal investigator (PI) will oversee and assume responsibility for subject safety monitoring. Data monitoring will be the responsibility of the PI in conjunction with the other investigators. A staff member during the course of the study will follow the progress of the study and data entry, to assure utmost accuracy of the data and to detect the possible errors at an early time point. The PI will review all the results. Participant safety data that will be monitored include any adverse experiences, although this is unlikely given the nature of yoga as discussed above.

BIBLIOGRAPHY

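### The Lay Summary plans to stratify HRQOL by disease response and remission, apparently judged after yoga starts; such strata cannot show who benefits from yoga

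*Combined protocol and SAP*

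**What the plan says.** The Lay Summary gives a purpose for the response and remission data: "Disease response and remission rates will be followed as well, in order to stratify HRQOL outcomes in the yoga group". It also treats disease response as something measured as a change: "Baseline and follow-up questionnaires will be used to determine there are changes in QOL, self-efficacy, and disease response".

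Section IV (Data collection measures) has the activity indices "collected at baseline and at the different endpoints (Impact III, peds QL, self efficacy scale, PCDAI, PUCAI"), so they are available both before and after yoga. Surveys are completed at consent (time 0), start of yoga (time 1), end of yoga (time 2) and three months later (time 3). The own-control contrast in Section IV compares the change from time 0 to time 1 with the change from time 1 to time 2, in all patients.

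Two further statements bear on the point. Section II says that "patients with increased disease severity often have worse HRQOL". Section IV says: "Through the entire study period patients will receive standard medical therapy as determined by their specific pediatric gastroenterologist".

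Section V covers "Clinical factors collected at baseline and post intervention" and sets significance at p < 0.05. It does not mention stratifying HRQOL, define response or remission, or say when either is judged.

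**The concern.** A stratifier is safe when it is fixed before the intervention starts. Response is a change in disease state, and rates that are followed over a study are normally known only later. If patients are sorted by what their disease did between time 1 and time 2, and HRQOL moves with disease activity, the sorting itself moves HRQOL up in one stratum and down in the other. Continuing medical therapy means that such a response can occur without any contribution from yoga.

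The instruments add to this. Impact III covers "IBD symptoms, systemic symptoms, emotional functioning, social functioning, body image, and treatment/interventions", and the activity indices also score patient symptoms, so stratifier and outcome partly measure the same thing.

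At stake is interpretation. A gain among responders could be read as showing the patients in whom yoga works, in a single-group study of 34 with no concurrent control against which to check that reading.

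**Working it through.** **Plan's own figure.** The plan gives none for the stratified analysis. From the Sample Size paragraph I take n = 34, SD 15.4 and the 10-point target as given. The paired formula with an SD of change of 15.4 gives ((1.960 + 0.842) × 15.4 / 10)² = 18.6, or 19 patients (21 with the t distribution), not 34. That is a separate matter, and nothing below depends on it.

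**Which reading of the strata is natural?** The Lay Summary follows response and remission over time and determines changes in disease response from baseline and follow-up data; Section IV collects the indices at later endpoints. Together these point to status judged after yoga starts. They do not settle it, because no time point is written down.

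**Assumptions that the documents do not give**
- True yoga effect zero.
- SD 15.4 at each time. The protocol states 15.4 as the SD of the score in a control group.
- Within-patient correlation 0.5 between any two times.
- Half the patients respond (17 of 34), split on disease-activity improvement from time 1 to time 2.
- Correlation r between that improvement and the HRQOL change over the same interval: 0.1 to 0.5.

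**Step 1: change from time 1 to time 2.** SD of change = 15.4 × √(2 × (1 − 0.5)) = 15.4. The mean of the upper half of a standard normal variable is 0.798. Expected responder change = r × 0.798 × 15.4, which is 1.2 at r = 0.1, 3.7 at r = 0.3 and 6.1 at r = 0.5.

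**Step 2: the protocol's contrast** (time 1–2 change minus time 0–1 change). The two changes share the time 1 score with opposite signs, so with equal correlations between times they correlate at −0.5. Responders are therefore expected to have had a time 0–1 change of −0.5 × the Step 1 value, and the contrast is 1.5 times Step 1:
- r = 0.1: 1.5 × 1.23 = 1.8
- r = 0.3: 1.5 × 3.69 = 5.5
- r = 0.5: 1.5 × 6.14 = 9.2

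Simulation with exactly 17 of 34 in the stratum gives slightly less at the upper end, about 9.0. Non-responders show losses of the same size.

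**Step 3: a paired test in the 17 responders, if one were run.** The SD of the contrast is 15.4 × √(6 × (1 − 0.5)) = 26.7, larger than in Step 1. Simulated rates of two-sided p < 0.05 in the direction of benefit (nominal 2.5%):

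| r | Protocol's contrast | Time 1–2 change alone |
|---|---|---|
| 0.1 | about 5% | about 5% |
| 0.2 | about 8% | about 9% |
| 0.3 | about 12% | about 15% |
| 0.5 | 28% to 29% | about 38% |

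The unstratified test in all 34 stays near its nominal 5% (two-sided) throughout.

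**Sensitivity of the mean on the protocol's contrast**
- Within-patient correlation 0.7: SD of change = 15.4 × √0.6 = 11.9, and the responder mean is 1.5 × r × 0.798 × 11.9, or 1.4 to 7.1.
- 30% responding: 0.798 becomes 0.348 / 0.30 = 1.159, and the mean is 1.5 × r × 1.159 × 15.4, or 2.7 to 13.4.

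The direction is the same for any positive r.

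**The case against.** The strongest reply is that no biased analysis has actually been planned. The sentence appears once, in the Lay Summary. The Specific Aims, the design comparison and Section V contain no stratified analysis, no within-stratum test and no claim about who benefits. The time point is undefined: remission status at time 0 or time 1, or response to standard therapy before the first class, would be a legitimate stratifier. Showing HRQOL by disease course may also be an innocent check on whether a gain merely tracks disease improvement. Finally, the correlations are assumed, and patients already inactive at the start cannot respond, so an even split is doubtful.

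Much of this stands, and it rules out several stronger readings that a reader might infer:
- That stratification is the only use of these data. The Lay Summary also treats disease response as a measured change, and Section V analyses clinical factors before and after the intervention.
- That response is caused mainly by medical therapy. The protocol says only that therapy continues.
- That the plan commits to testing within responders. It does not; the test above is hypothetical.
- That strata formed after yoga starts are an established fact. That is the natural reading, but it is not written.

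What does not stand is the suggestion that placement in the Lay Summary disposes of the point. It is part of the protocol and states a purpose, and Section V neither withdraws nor limits it. The own-control period does not remove the bias either: Step 2 shows that it enlarges the mean shift, although the wider SD lowers the false-benefit rate. A descriptive check would be unobjectionable, but the protocol does not say that this is the intent.

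**Conclusion.** The point holds in limited form. Followed as written and read naturally, the Lay Summary sentence produces strata in which an HRQOL gain among responders is expected without any yoga effect. Those strata cannot show who benefits. The mechanism rests on the protocol's own statements.

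The size does not. Zero yoga effect, within-patient correlation 0.5, half responding and r from 0.1 to 0.5 are assumptions. Under them the spurious responder gain is about 1.8 to 9.0 points, against a 10-point target, with false benefit in roughly 5% to 28% of trials if a test were run. At the low end the distortion is small.

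A reader might infer that the trial's main result is compromised. It is not: that comparison uses all patients and is unstratified. This is a cheap improvement of minor priority.

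**What to change.** Replace the Lay Summary sentence, and add matching text to Section V, along these lines:

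- HRQOL change will be summarised by disease activity at time 1, inactive versus active, using PCDAI/PUCAI or the Physician Global Assessment. State which measure is used, how inactive is defined, and how close to time 1 the chart assessment must be. The gastroenterologist clearance required within 8 weeks before yoga is a possible source.
- Response and remission will be defined and reported as outcomes in their own right, over both time 0–1 and time 1–2.
- Any table of HRQOL by response will be labelled descriptive, with no p-value and no statement about who benefits.

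The cost is wording, since the activity measures are already to be collected. The only loss is the option of a significance test by response, which could not be interpreted as a yoga effect anyway.

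### The own-control contrast described in the Methods is never tied to the primary aim, and Section V replaces it with a two-group comparison that this single-arm design cannot run

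*Combined protocol and SAP*

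**What the plan says.** The primary aim (I. Specific Aims) is to find out whether yoga improves health-related quality of life (HRQOL). It names no instrument, time point or contrast. Four other places bear on how the aim will be judged.

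- **IV, Participants and Enrollment.** Surveys are taken at consent (T0), start of yoga (T1), end of yoga (T2) and three months later (T3). Patients act as their own controls, and the section describes this contrast: "difference between time of enrollment (time 0)/start of yoga (time 1) and start of yoga (time 1)/end of yoga (end of 2) being compared". This is the only explicit time contrast in the document.
- **IV, Sample Size.** With 34 patients "there will be 80% power to detect a 10-point increase (improvement) in average total PedsQL score". The inputs are a control-group SD of 15.4 for the total score, "probability of Type I error (alpha) of 0.05" and "probability of Type II error (beta) of 0.20". No time points are attached to the 10 points.
- **V. Planned Data Analysis.** "Clinical factors collected at baseline and post intervention and the differences will be" compared, the sentence goes on, between a yoga group and a control group. The named tests are a t-test (type not given) and, if normality fails, Mann-Whitney U. No paired or repeated-measures method is named, and the Section IV contrast is not mentioned.
- **Lay Summary, closing paragraph.** "Baseline and follow-up questionnaires will be used to determine there are changes in QOL, self-efficacy, and disease response". Neither baseline nor follow-up is defined.

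**The concern.** The T0 survey lets the trial separate change during yoga from change that would have happened anyway. Such change is plausible: standard medical therapy continues throughout, and patients must be cleared by their gastroenterologist shortly before yoga starts. The T0 survey helps only if the deciding analysis uses the T0 to T1 interval.

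The analysis section does not say that it will. Its two-group wording does not fit a single-arm trial, so whoever analyses the data must reinterpret it. Three quantities are then within reach:

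- T2-T1, which has no control for drift;
- T2-T0, which also includes anything gained before the first class;
- (T2-T1)-(T1-T0), which subtracts the waiting period.

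They estimate different things and can disagree on the same data. If the analyst keeps Section V's independent-groups tests and applies them to the two interval changes, the standard error is also wrong.

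**Working it through.** **Inputs.** From IV, Sample Size: n = 34, SD 15.4, alpha 0.05, power 80%, difference 10. Assumed, because the documents do not give them: two-sided tests, an equal correlation r between visits, and the size of any drift.

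**1. Does the stated n show which contrast was meant?**
- Paired, taking 15.4 as the SD of the change: (15.4 × (1.960 + 0.842) / 10)² = 18.6, so 19 patients, or 21 with the t distribution. This is not 34.
- Two independent groups: 2 × 18.6 = 37.2, so 38 per group. This is not 34 either.
- A two-sided paired t-test with n = 34 and 80% power needs an SD of about 20.2. A plain change gives 15.4 × √(2(1-r)) = 20.2 at r ≈ 0.14. The difference of changes gives 15.4 × √(6(1-r)) = 20.2 at r ≈ 0.71.

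The figure of 34 is not reproduced from the stated inputs, and it could fit either contrast.

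**2. False benefit under drift.** There is no yoga effect, r = 0.5 and the nominal rate for benefit is 2.5%. The SD of a plain change is 15.4 × √(2 × 0.5) = 15.4, so SE = 15.4/√34 = 2.64. The critical t on 33 df is 2.035. With 3 points of drift per interval, the noncentrality is 3/2.64 = 1.14 for T2-T1 and 6/2.64 = 2.27 for T2-T0. For (T2-T1)-(T1-T0) it is 0 when the intervals are equal.

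| Scenario (r = 0.5) | T2-T1 | T2-T0 | (T2-T1)-(T1-T0) |
|---|---|---|---|
| Drift 3 per interval | 20% | 60% | 2.5% |
| Drift 5 per interval | 45% | 96% | 2.5% |
| Gain of 5 in the wait only | 2.5% | 45% | 0.1% |

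Over r = 0.3 to 0.7, a drift of 3 points gives 15-30% for T2-T1 and 46-81% for T2-T0.

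**3. Free choice with no drift.** In simulation at n = 34, at least one of the three contrasts favours yoga significantly in about 5.5-6% of trials, against 2.5%.

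**4. Section V's tests applied to the two interval changes.** Each change has variance 2σ²(1-r). They share T1, so their covariance is -σ²(1-r). The true variance of their difference is (2 + 2 + 2)σ²(1-r) = 6σ²(1-r). An unpaired test assumes 4σ²(1-r), so its SE is too small by a factor √(4/6) = 0.82. Simulated two-sided error with no change at any visit is about 11% for r between 0.3 and 0.8, instead of 5%.

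**5. Power if the own-control contrast decides** (10-point difference, paired t, two-sided 0.05):

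| r | SD of contrast | Power at n = 34 | n for 80% |
|---|---|---|---|
| 0.3 | 31.6 | 43% | 81 |
| 0.5 | 26.7 | 56% | 58 |
| 0.7 | 20.7 | 78% | 36 |

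**6. Unequal intervals.** Suppose drift is 5 points per 12 weeks and the wait is 4 weeks (both assumed). The contrast then keeps 5 - 5 × 4/12 = 3.3 points of drift. False benefit is about 9%, 11% and 15% at r = 0.3, 0.5 and 0.7.

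**The case against.** The best defence is that Section IV already settles the matter. It is the most specific text, it names both intervals, and no passage states T2-T1 or T2-T0 alone as a test. Section V's control could be read as each patient's own waiting period. Its sentence concerns clinical factors rather than HRQOL by name.

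Much of this stands, and it rules out some stronger readings that a reader might infer:

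- *Section V prescribes an uncontrolled before-after test.* It does not. The full sentence describes a comparison with controls; the trouble is that the control group it refers to does not exist here.
- *The plan offers three equally supported rival contrasts.* It does not. The Lay Summary line is general wording, in a paragraph that itself calls patients their own controls. The 10-point increase is an effect size without time points, not a further contrast.
- *Free choice gives a false claim of yoga benefit in 11-12% of trials.* That figure counts significant worsening as well. For false benefit the rate is about 5.5-6% against 2.5%, and it presumes that all three contrasts are tested.

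The defence does not close the gap. The Section IV contrast is not carried into the aim, the sample size or Section V. Even on the charitable reading, Section V names no paired test, and Mann-Whitney is an independent-groups test.

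**Conclusion.** The point holds in limited form. The plan contains one sound own-control contrast, but nothing makes it decisive for the primary aim, and the analysis section gives a two-group comparison that cannot be run as written. A plain T2-T1 or T2-T0 change could be reported as the yoga effect without departing clearly from the plan.

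The size depends on assumptions. The 20% and 60% rates need a steady 3-point drift and r = 0.5, neither of which is in the documents. The 11% error from unpaired testing needs no drift but does assume equal correlations. A gain confined to the wait misleads only a contrast that starts at T0; T2-T1 is unaffected and the own-control contrast moves against yoga. The own-control contrast is not immune either: classes run twice a year and T0 is the date of consent, so the wait is not fixed and some drift can remain.

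**What to change.** In Section V, name as the deciding analysis the within-patient mean of (T2-T1)-(T1-T0) in PedsQL total score, the instrument used for the sample size. Test it with a one-sample (paired) t-test, or the Wilcoxon signed-rank test if normality fails, at two-sided 0.05. Report T2-T1 and T2-T0 as descriptive estimates with 95% confidence intervals. Remove the control-group wording, define baseline as T0 for the waiting interval and T1 for the yoga interval, and bring the Lay Summary and Section IV into line. Record the length of each patient's wait and add a sensitivity analysis based on change per week.

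The cost is mainly power. The wording changes need no new questionnaires, but the stated 80% cannot simply be carried over. The sample size must be restated with the SD of this contrast and a justified correlation, with either a larger n or an open statement of the lower power. Full removal of steady drift still requires equal intervals, so that limitation should be stated.
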